COVER PAGE

Official Title of the Study

Intrapartum epidural catheter displacement: Comparison of three dressing methods in morbidly obese parturients

NCT Number

NCT03574441

Protocol Title: *Intrapartum epidural catheter displacement: Comparison of three dressing methods in morbidly obese parturients*

Principal Investigator: *[name] MD*

1. Objectives

Purpose, specific aims, and hypothesis:

Purpose: We propose this study to prospectively evaluate the efficacy of the three types of epidural catheter dressings that we currently use in our Labor and Delivery unit, in terms of catheter migration, taking into consideration the influence of body mass index on this variable.

Primary aim: We will evaluate the efficacy of three different epidural catheter dressing systems in laboring patients.

Secondary aims: To compare the effect of different degrees of obesity measured by BMI, on epidural catheter migration and quality and failure of epidural labor analgesia. To evaluate the effect of time an indwelling catheter remains in place, level of insertion and patient's height on epidural catheter migration.

Hypothesis: The use of dressing with transparent TegadermTM plus SorbaView SHIELD® dressing is superior to the dressing with TegadermTM plus Steri-StripTM bands in addition to a catheter support pad, and to a dressing with TegadermTM only, for epidural catheter fixation in laboring obese and morbidly obese patients, in terms of catheter migration, epidural quality and failure and epidural catheter replacement in the labor analgesia setting.

2. Background

Background and rationale for the study:

Failure of labor epidural is a well-recognized situation in obstetric anesthesia practice. Incidence of epidural failure was shown to be 12% in a retrospective analysis of 19.259 deliveries (1). Epidural migration has been documented in both the obstetric and non-obstetric settings (2,3). It has been argued that prevention of epidural displacement is a potential remedy to at least part of the incomplete or failed epidurals in obstetrics (4,5). Motamed et al showed that 45% of epidural failures in major abdominal surgery could be attributable to catheter migration (6). Phillips et al studied epidural catheter migration in labor finding an incidence of 54% (7). Migration was 2 cm on average and tended to be directed inward. Crosby et al found a similar incidence of catheter migration but in an outward direction (8).

Factors influencing catheter migration include weight, body mass index, depth of the epidural space and patient positioning (9,10). Bishton et al documented inward migration in 13% and outward displacement of one or more centimeters in 22% of patients in a cohort of 153 laboring patients (10). They also found that all cases of failed epidural occurred in patients with outward migration greater than 2,5 cm (10). Hamilton et al showed an association between patient position change and movement of epidural catheters, when the patient is sitting with a straight back and when placed on lateral decubitus position (11). The authors found that the magnitude of epidural catheter movement was more pronounced in patients with $BMI > 30 \text{ kg/m}^2$. It has been hypothesized that the epidural catheter might be fixed to the ligamentum flavum after it is threaded, as the maximum pressure found during catheter placement corresponds to this anatomical structure (12). When the patient changes position after taping the catheter, especially in the case of a parturient with high BMI, the new anchor point theoretically moves to the skin, facilitating outward migration of the epidural catheter (9).

Some authors have evaluated the influence of different dressing methods on epidural catheter migration. Burns et al compared Tegaderm™ dressing, Tegaderm™ plus filter-shoulder fixation and Niko Epi-Fix dressing in 113 patients in labor (2), finding that Tegaderm™ plus filter-shoulder was superior in terms of minimization of epidural catheter displacement. Their study doesn't mention weight or BMI of patients included in the study. Odor et al evaluated the efficacy of Epi-Fix™, Lockit Plus® and Tegaderm™ for dressing of intrapartum catheters, finding superiority of the Lockit Plus® system to decrease catheter migration and epidural analgesic failure (13). The authors didn't evaluate the effect of BMI on the outcomes and even excluded patients with $BMI > 50 \text{ kg/m}^2$. Similar results were reported by Clark et al in a cohort of 102 patients having epidural catheters for major non-obstetric procedures (14).

The obstetric population treated at the Labor and Delivery Unit at Augusta University Medical Center is characterized by a high incidence of obesity and morbid obesity. This situation makes insertion and management of epidural labor analgesia catheters particularly challenging. Although the influence of BMI on catheter migration has been suggested; to our knowledge, no study to date has evaluated epidural catheter migration in a high BMI obstetric population. Evaluating these type of association is clinically relevant as epidural failure is a situation that might potentially compromise patient safety. It may increase the rate of epidural replacement with the concomitant technical difficulties and the potential need to use general anesthesia in cases of unplanned cesarean section in a patient with an indwelling epidural catheter. This latter situation is particularly hazardous, knowing the increased incidence of difficult airway in both obstetric and obese patients (15). We propose this study to compare the effect of three different epidural catheter dressing systems in patients with $BMI > 30 \text{ kg/m}^2$ on epidural catheter migration and epidural quality and failure in the labor analgesia setting.

3. Inclusion and Exclusion Criteria

Inclusion criteria will be the following:

- 1) Patients admitted to the Labor and delivery Unit at Augusta University Medical Center who request epidural analgesia.
- 2) $BMI > 30 \text{ kg/m}^2$.
- 3) Age older than 18 years old.

Exclusion criteria are the following:

- 1) Allergy to adhesive tape or to the components of the dressings used in the study.
- 2) Preexisting sensory neurologic deficits affecting lower extremities.
- 3) Patients taken to the operating room for cesarean section during the study period.
- 4) Chronic pain conditions.
- 5) Patients with intrathecal catheters.

4. Number of Subjects/Records/Samples Collected

Total number of subjects to be accrued/records reviewed/samples collected:

Based on previous experiences for a measurable difference of 0,5 cm, we will include 35 patients in each group to have a power of 90% and a statistical significance level of 0,05.

5. Recruitment Methods

Recruitment methods:

Patients who request labor epidural and fulfill inclusion criteria will be included in the study and randomly assigned to one of the three study groups.

6. Procedures Involved

- a. *Procedures involved to include those procedures that are standard evaluation and/or care and those that are solely for research purposes:*

After approval by the Institutional Review Board, we will obtain consent from the participant patients. Patients will be randomized using a random number table to be allocated to one of three groups with sealed envelopes, based on the type of dressing to be used to secure the epidural catheter after its insertion:

- 1) Tegaderm™ plus SorbaView SHIELD® dressing
- 2) Dressing with Tegaderm™ plus Steri-Strip™ bands in addition to a catheter support pad (All included in the epidural kit)
- 3) dressing with Tegaderm™ only

Patients will have an epidural catheter placed for labor. We will use the standard epidural kit (Smiths Medical ASD Inc. Keene, NH. USA). The technique will consist of the use of a 17G Tuohy needle using a midline

approach with the patient in the sitting position. Localization of the epidural space will take place using loss of resistance to air or saline per anesthesiologist's preference. A 20G epidural catheter will be inserted to leave 5 cm into the epidural space (distal to the tip of the Tuohy needle). After the Tuohy needle is removed and the catheter is considered to be at an adequate depth, the patients will be asked to sit up straight. Then, a test dose with 3 mL of Lidocaine 1,5% with epinephrine 1:200.000 will be injected through the catheter into the epidural space, and a dressing varying depending on the assigned group will be applied. The rest of the catheter will be secured longitudinally along the patient's back over the shoulder.

b. Study design:

This is a randomized controlled clinical trial.

c. Procedures performed to lessen the probability or magnitude of risks:

The application of the three types of epidural dressings analyzed in this study are part of our current standard clinical practice. There is no additional risk due to our intervention. We will protect the rights of the patient maintaining confidentiality (records will be de-identified and assigned a study number) and patients can revoke their consent to participate at any moment during the study. Visual evaluation of the site of insertion of the epidural catheter will be inspected during the study period and any signs of topical or allergic reactions to any of the components used for dressing will be identified and treated accordingly should it happen.

d. Duration of an individual subject's participation in the study and the time involved:

The patients will be participating in the study for as long as the epidural catheter remains in place for clinical indications. The expected time will be between 6 and 12 hours.

7. Data and Specimen Management

a. Data analysis plan:

Sample size: Based on previous experiences for a measurable difference of 0,5 cm, we will include 35 patients in each group to have a power of 90% and a statistical significance level of 0,05. Data will be analyzed using analysis of variance, Student's t test, chi-square test and Pearson's correlation coefficients where appropriate.

N/A

b. Power analysis:

See above

N/A

c. Data handling:

N/A

i. Information included in the data

Following dressing application, demographic variables of each patient will be recorded including (age, gravity, parity, weeks of gestation, weight, height, BMI). Other recorded variables include time of insertion, distance from catheter tip to skin in centimeters. One hour after delivery, immediately before catheter removal, time, duration of catheter presence, centimeters from skin to catheter tip and dressing integrity will be recorded. Dermatomal level and symmetry of the block will be recorded every two hours or every time the patients requires a top-up dose. We will also record number of top up doses and rate of epidural infusion as well as the need for catheter replacement during the observation period.

Primary outcomes

Epidural catheter migration (ECM) in centimeters = Distance from tip to skin at insertion - Distance from tip to skin at removal. If the catheter moves inward, ECM will be negative and if it gets displaced outwardly, ECM will be positive.

Secondary outcomes

- 1) Dermatomal sensory level measured with thermal discrimination
- 2) Incidence of asymmetric block
- 3) Rate of epidural catheter replacement
- 4) Total epidural dose (mL)
- 5) Number of top-up epidural boluses.

ii. Data storage

Data derived from the study will be stored in a locked drawer in the office of the PI for the duration of the study. The de-identified information will be accessed by the research team and the statistician for analysis.

iii. Duration of data storage

For one year after study completion.

iv. Access to data

The PI and the research team.

v. Responsible for receipt or transmission of the data

The Principal Investigator

vi. Data transport

From the site of data collection to the PI office by the Principal Investigator.

8. Provisions to Monitor the Data to Ensure the Safety of Subjects

a. Data safety and delivery plan

The Principal Investigator (PI) will be responsible for the conduct of this study, including overseeing participant confidentiality, executing the Data and safety Monitoring (DSM) plan, and complying with all reporting requirements to local and federal authorities. This oversight will be accomplished through additional oversight from a Data and Safety Monitoring Committee at the Augusta University. We will conduct ongoing review of all serious adverse events (SAEs), unanticipated problems (UAPs) and reportable adverse events (AEs). Per the DSM Plan, SAEs, UAPs and reportable AEs will be reported to the institutional committee and IRB per study protocol. All SAEs, UAPs and reportable AEs are to be reported to the committee and IRB within 5 business days of receiving notification of the occurrence.

Audits will consist of a review of the regulatory documents, consent forms, and source data verification. Results and recommendations from audits will then need to be submitted by the PI to the IRB of record at the time of the continuing review.

b. Data review.

We will review the results for analysis at the end of data collection. The participants will be informed from the beginning of the study that any concerns related to the study be communicated directly to the PI, who will address them according to the DSM plan.

c. Collection of safety information

Data will be de-identified right after collection and be kept as paper record in the PI office.

d. Frequency of data collection

Data will be collected daily.

e. Responsible of data review.

The research team (PI and 2 co-investigators) will collect and analyze data.

f. Frequency of data review

Every week there will be a review of the cumulative data.

g. Conditions that trigger an immediate suspension of the research.

N/A

9. Withdrawal of Subjects

N/A

a. Anticipated circumstances under which subjects will be withdrawn from the research without their consent.

Patients will be withdrawn from the study if she develops an allergic or topical reaction to dressing or if the dressing has to be replaced due to soiling or bleeding.

N/A

b. Procedures for orderly termination.

N/A

If during the preliminary data review one of the dressings is performing significantly better or worse than the others, or if one of the groups has higher incidence of catheter migration than that reported in the literature, the study will be terminated and the results analyzed up to that point.

c. Procedures that will be followed when subjects withdraw from the research

N/A

If there is withdrawal of consent or if a subject is withdrawn without consent for the circumstances cited above, those cases will be included in the analysis as "lost to follow-up" and reported in the results section.

10. Risks to Subjects

a. *Foreseeable risks.*

No risks additional to standard clinical care are foreseen. Topical or allergic reactions to the dressing materials would be managed by removal of the dressing and topical treatments.

b. *Costs that subjects may be responsible for because of participation in the research.*

N/A

N/A

c. *Risks to others who are not subjects.*

N/A

N/A

11. Potential Benefits to Subjects

There is no direct benefit to patients expected from their participation in this study. It is hoped the knowledge gained will be of benefit to other patients in the future.

12. Confidentiality

Procedures for maintenance of confidentiality.

See above

13. Consent Process

Before enrollment in the study, patients will be explained the purposes of the study, the risks and the procedures that will take place as part of the study. Time will be given to answer questions and PI contact information will be provided. Then, the patient will be given the opportunity to decide about participation in the study by signing the consent. The possibility of revoking the consent at any time during the study will also be explained (See consent form for details)..

14. Compensation for Research-Related Injury

This section is not required when research involves no more than Minimal Risk to subjects. **N/A**

a. *Describe the available compensation in the event of research related injury.*

N/A

15. Resources Available

N/A

a. *Availability of medical or psychological resources that subjects might need as a result of an anticipated consequences of the human research.*

N/A

b. *Process to ensure that all persons assisting with the research are adequately informed about the protocol, the research procedures, and their duties and functions.*

The PI and the two co-investigators will collect and analyze data and are fully aware of the protocol as they participated in its construction. A statistician will assist with analysis and he will have access to tabulated de-identified information.

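### BMI is named as a driver of catheter migration and is recorded, but neither the randomisation nor the planned tests take it into account when dressings are compared

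*Combined protocol and SAP*

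**What the plan says.** - **Allocation (Section 6.a):** "Patients will be randomized using a random number table to be allocated to one of three groups with sealed envelopes". Section 5 adds only that women are "randomly assigned to one of the three study groups". Neither section gives a block size, a stratification factor, or the number of envelopes prepared for each arm.
- **Sample size (Sections 4 and 7.a):** the target is a difference of half a centimetre, taken from earlier experience, for which "we will include 35 patients in each group to have a power of 90% and a statistical significance level of 0,05". No standard deviation is given.
- **Analysis (Section 7.a):** "Data will be analyzed using analysis of variance", together with the t test, the chi-square test and Pearson correlation where suitable. No model with a covariate is named.
- **Role of BMI:** Section 2 lists it among the influences on migration. The purpose statement in Section 1 says its influence will be considered, and a secondary aim is "To compare the effect of different degrees of obesity measured by BMI, on epidural catheter migration". Section 7.c.i records weight, height and BMI for each woman.
- **Population:** the title reads "Comparison of three dressing methods in morbidly obese parturients", but Section 3 admits any woman with BMI above 30, and no section gives a cut-off for morbid obesity.

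**The concern.** The protocol treats BMI as prognostic for its own primary outcome, epidural catheter migration (ECM) in centimetres. A prognostic baseline variable can be handled in two places: balanced at randomisation, or included in the analysis model. The plan as written does neither for the dressing comparison. Pearson correlation can describe how BMI relates to migration, but it does not adjust the difference between dressings.

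Precision is what is at stake. Variation in migration that BMI could explain stays in the error term. In any one trial, a chance difference in BMI between arms moves the observed dressing difference with nothing in the plan to correct it. Readers who see an uneven baseline table would also have no prespecified adjusted result to turn to.

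**Working it through.** **1. The plan's own figure.** For two arms of size n, a two-sided test and the normal approximation, SD = d × √(n/2) / (1.960 + 1.282). With d = 0.5 cm and n = 35, SD = 0.5 × 4.183 / 3.242 = 0.645 cm. The documents give no SD, so 35 per group cannot be confirmed. The value 0.645 cm is back-calculated, and every power figure below uses it.

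**2. BMI imbalance with arm sizes fixed at 35.** This case is the most favourable to the plan on arm size, and it needs no assumption that allocation is unrestricted. If M of the 105 women are morbidly obese, their split over three arms of 35 follows a multivariate hypergeometric distribution. The share is not in the documents, so M is varied. The last column shows simple 1:1:1 allocation for comparison.

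| M of 105 (assumed) | Gap of 6 or more between largest and smallest arm, arms fixed at 35 | Same, simple allocation |
|---|---|---|
| 21 | 22% | 30% |
| 30 | 31% | 43% |
| 42 | 37% | 55% |

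Fixing the arm sizes reduces the imbalance but does not remove it.

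**3. What adjustment returns.** If r is the within-arm correlation between BMI and ECM, including BMI in the model reduces the residual SD to 0.645 × √(1 − r²). Pairwise power is Φ(0.5 / (SD × √(2/35)) − 1.960).

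| r (assumed) | Residual SD (cm) | 0.5 / standard error | Power |
|---|---|---|---|
| 0 | 0.645 | 3.243 | 90.0% |
| 0.2 | 0.632 | 3.310 | 91.1% |
| 0.3 | 0.615 | 3.399 | 92.5% |
| 0.4 | 0.591 | 3.538 | 94.3% |

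The unadjusted analysis would need 35 / (1 − r²) women per arm to match: 36.5 at r = 0.2 and 41.7 at r = 0.4. The model spends one error degree of freedom of about 100, which is negligible.

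**4. Arm sizes, only if allocation is simple.** With 105 women, P(35/35/35) = 105! / (35!)³ / 3¹⁰⁵ = 0.8%, and the smallest arm is below 30 in 37% of trials. Pairwise power then averages 89.4%, with a 5th percentile of 85.5%. The mean loss is about 0.6 points.

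**5. Morbidly obese women alone.** Suppose 42 are enrolled. An even 14/14 pair gives 0.5 / (0.645 × √(2/14)) = 2.051 and power of about 54%. An 11/17 pair gives 2.003 and about 52%.

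**The case against.** **Unstratified randomisation is legitimate.** In a trial of 105 women, chance imbalance in BMI neither biases the dressing comparison in expectation nor inflates type I error. BMI is collected at baseline, so adjustment remains possible. All of this stands, and it is why the point is minor. It does not answer the remaining gap: an adjusted analysis that is possible but not prespecified is a choice left until the data are seen.

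**Enrolment only above BMI 30 narrows the BMI range.** The correlation with migration could be weaker than assumed. That also stands. At r = 0 the gain is nil, and the cost is one degree of freedom.

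A reader might infer two stronger claims, and the documents support neither.

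- *That allocation is simple, so 35 per group will almost never occur.* A random number table supplies digits; it is not a scheme. It can order 35 prepared envelopes per arm or generate permuted blocks, and the commitment to 35 in each group fits either. The text is silent on restriction, so the 0.8% is conditional. Even if the condition holds, the mean power loss is small.
- *That stratifying would rescue a comparison among morbidly obese women.* Stratification evens out their split but does not add to their number. By step 5, power is about 54% with a perfect split and about 52% with an uneven one. The stated BMI aim relates degree of obesity to migration across all women and does not need equal counts per arm.

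**Conclusion.** The point holds as a modest loss of precision. BMI is declared prognostic and is recorded, yet it is absent from both the described randomisation and the planned comparison of dressings, however the random number table is used. Substantial chance imbalance is quite likely: a gap of 6 or more morbidly obese women in about 31% to 37% of trials with arms fixed at 35, if 30 to 42 of 105 are morbidly obese. The recoverable power is about 1 to 4 points for r between 0.2 and 0.4.

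These sizes rest on three things that the documents do not give: the share of morbidly obese women, the BMI–migration correlation, and the SD, for which 0.645 cm is back-calculated. The finding does not show bias or an inflated error rate, and it does not establish that allocation is unrestricted.

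**What to change.** **Main change.** In Section 7.a, name as the primary analysis a linear model (ANCOVA) for ECM with dressing group and continuous BMI, and report adjusted differences between dressings with confidence intervals. BMI is already collected, so the cost is one sentence in the plan and one degree of freedom.

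**Reporting.** In Section 6.a, state the type of randomisation, any restriction, and how many envelopes are prepared.

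**Optional.** Prepare two sequential envelope sets by BMI class, using a cut-off that the protocol defines, each in permuted blocks of varying size (for example 3 and 6) unknown to enrolling staff. With blocks of 3 throughout, counts of morbidly obese women would differ by at most 1 between arms and arm totals by at most 2; with blocks of 6, by at most 2 and 4. The cost is preparing the second set before the start, and slightly more predictable allocation if those applying the dressings can see them, which varying the block size limits.

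Blocks would not secure 35 evaluable women per arm. Caesarean section (Section 3) and dressing replacement (Section 9.a) can remove women after randomisation, and the sample size makes no allowance for that.

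### Section 7a does not say how BMI enters the dressing comparison, although the stated purpose is to take BMI into account; the loss is precision, not validity

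*Combined protocol and SAP*

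**What the plan says.** Section 1 (Objectives) states the purpose as evaluating the three dressings on catheter migration, "taking into consideration the influence of body mass index on this variable". A secondary aim is "To compare the effect of different degrees of obesity measured by BMI, on epidural catheter migration and quality and failure of epidural labor analgesia". A further aim covers dwell time, insertion level and patient height: "To evaluate the effect of time an indwelling catheter remains in place, level of insertion" and so on.

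Section 2 (Background) gives the reason for the interest in BMI: "Factors influencing catheter migration include weight, body mass index, depth of the epidural space and patient positioning".

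Section 7c.i lists weight, height and BMI among the variables recorded after the dressing is applied. Catheter duration is recorded at removal.

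Apart from the sample size statement, section 7a consists of one sentence on method: "Data will be analyzed using analysis of variance, Student's t test, chi-square test and Pearson's correlation coefficients where appropriate". It does not match methods to aims, and it names no covariate, BMI factor, stratum or regression model. Section 6a describes randomisation with a random number table and sealed envelopes and mentions no stratification by BMI.

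**The concern.** BMI is the feature that sets this trial apart from the earlier dressing studies that the Background discusses. The plan treats BMI as a likely driver of the primary outcome and collects it in every patient. It does not say what will be done with it when the dressings are compared.

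Two things are at stake. First, a baseline variable related to the outcome can narrow the confidence intervals for the dressing contrasts at almost no cost, and the plan as written does not secure that. Second, "where appropriate" leaves open whether BMI is ignored, used as a class variable or used as a covariate. A choice of that kind is better fixed before the data are seen.

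A related difficulty affects the secondary aims. Height is one of the predictors of interest, and BMI is computed from height. A correlation of height with migration therefore cannot be taken at face value as an effect of height.

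**Working it through.** **Inputs from the plan (sections 4 and 7a).** 35 patients per group, difference 0.5 cm, power 90%, significance level 0.05. No SD is given and sidedness is not stated.

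**Assumptions.** Two-sided test; pairwise t test; correlation r between BMI and migration, within BMI > 30, from 0 to 0.5.

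**Step 1: the plan's own figure.** Without an SD, 35 per group cannot be reproduced, so I solve for the SD that it implies. The non-centrality is 0.5 / (SD × √(2/35)), with 68 degrees of freedom. Power of 90% requires a non-centrality of about 3.29. Then SD = 0.5 / (3.29 × 0.239) = 0.636 cm. The normal approximation gives 0.645 cm.

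**Step 2: effect of adding BMI.** Residual SD = 0.636 × √(1 − r²), with 67 degrees of freedom for power. At r = 0.3 this is 0.636 × 0.954 = 0.607 cm. The non-centrality becomes 0.5 / (0.607 × 0.239) = 3.45, and power is 92.5%. The interval half-width is t × residual SD × √(2/35), using the error degrees of freedom from all three arms (102 without BMI, 101 with it).

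| Assumed r | Power with BMI | 95% CI half-width (cm) |
|---|---|---|
| 0 | 90.0% | 0.302 |
| 0.1 | 90.3% | 0.300 |
| 0.2 | 91.1% | 0.296 |
| 0.3 | 92.5% | 0.288 |
| 0.4 | 94.2% | 0.276 |
| 0.5 | 96.3% | 0.261 |

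A simulation that allowed for chance BMI imbalance between arms gave adjusted power within about 0.1 point of these values. Unadjusted power in the same simulation, with the pooled three-arm error term, was about 90.3%. The gain is therefore nil at r = 0.1, about 1 point at 0.2, 2 at 0.3 and 6 at 0.5.

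**Step 3: fewer analysable patients.** If cesarean exclusions and dressing-replacement withdrawals left an assumed 28 per group, power would be 82.3% unadjusted, and 82.7% to 91.5% adjusted for r = 0.1 to 0.5.

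**Step 4: height.** Suppose migration depends on BMI alone. The induced height correlation is then r(BMI, migration) × r(BMI, height). With assumed values this runs from 0.3 × (−0.2) = −0.06 to 0.5 × (−0.4) = −0.20. The critical value at 105 patients is 0.192, and a Pearson test of height is nominally significant in about 9% to 54% of trials. If BMI and height are almost uncorrelated, the rate is close to 5%. Under this mechanism, a regression with BMI and height together restores about 5%.

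Now suppose weight, which the Background lists separately, is the driver. At a fixed BMI, weight = BMI × height², so taller women weigh more and the joint regression assigns weight's effect to height. I assumed height 162 (SD 6.5) cm, weight 100 (SD 20) kg, BMI > 30 and a weight-height correlation of 0 to 0.5. The joint model then flags height falsely in about one third of trials if weight and migration correlate at 0.3, and in about 80% if they correlate at 0.5. The single Pearson test does so in about 7% to 36% and 11% to 77%. Neither analysis isolates height under both mechanisms.

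**The case against.** The strongest reply is that nothing is broken. Section 1 does not promise covariate adjustment of the dressing contrast. BMI is also taken into account through the entry criterion and the secondary aim. Analysis of variance, applied where appropriate, could include dressing by obesity class. Randomisation makes the unadjusted comparison valid. Every correlation used above is assumed, and BMI is restricted to values above 30, which may weaken its relation to migration.

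Most of this stands. It is fair to say that the role of BMI is unspecified, and too strong to say that the plan excludes it. At r = 0.2 or below the gain is about one point or less. What remains is that the text does not state the model, although the variable is in hand and specifying its use costs almost nothing.

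A reader might also infer that separate correlations are the flaw and that one regression with BMI and height would cure it. Step 4 shows that this holds only if BMI alone drives migration, and the Background does not support so narrow a mechanism.

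Nor should a reader infer that insertion level will not be collected because section 7c.i does not name it. That list is open-ended: "Other recorded variables include time of insertion, distance from catheter tip to skin in centimeters". Naming it is a clarification only.

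**Conclusion.** The point holds as a minor one. Section 7a specifies no role for BMI in a dressing comparison whose stated purpose is to consider it. A reader might conclude that the unadjusted comparison is biased or invalid; the documents do not support that, because allocation is randomised. The loss is precision: from nothing at r = 0 to about 6 points of power and 0.04 cm of interval half-width (0.302 − 0.261) at r = 0.5. These sizes rest on an SD of 0.636 cm back-calculated from the plan's sample size, on a two-sided test, and on correlations that the documents do not give.

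For the secondary aims, a height correlation cannot be read as an effect of height in its own right. How often it would mislead depends on unknown correlations and on whether BMI or weight is the driver.

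**What to change.** In section 7a, specify the following:

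- The primary analysis of migration is a linear model on dressing (three levels) plus continuous baseline BMI.
- The SorbaView dressing is compared with each of the other two, with 95% confidence intervals.
- Dwell time stays out of this model, because it arises after randomisation.
- The unadjusted analysis of variance is reported as sensitivity.
- The BMI coefficient from this model serves the secondary aim on BMI and migration.
- Height results are reported as exploratory associations, whether from a correlation or from a model that also contains BMI.

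As a clarification, name vertebral insertion level in the section 7c.i list.

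The cost is a few lines of text and one residual degree of freedom: 102 to 101 with all 105 patients, or 81 to 80 with an assumed 28 per group. No new measurement is needed for the primary model. If BMI is not prognostic above 30 kg/m², there is no gain and practically no loss.
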